HIV-risk behavior	HIV-transmission-risk behavior (1°)	Condomless anal sex acts with HIV-positive or unknown-status partners outside of the context of one’s own adherent PrEP use or only with a primary partner that has adherent PrEP use or has undetectable viral load. This is measured with an online self-administered Timeline Follow-Back (TLFB) instrument. The TLFB yields past-30-day incidence of HIV risk behavior in terms of type of sexual behavior, condom use, partner(s) HIV status, self and partner adherent PrEP use (at least 4 days per week), sex while using drugs or alcohol, and number of sexual partners. HIV risk behavior acts as defined above will be measured as the pooled number (count) over 30 days prior to the 4-, 8-, and 12-month follow-up visits. A primary supportive analysis of this outcome will assess the above as any such behavior (binary) during the 30 days prior to the 4-, 8- and 12-month follow-up visits.
Mental health and substance use	Depression (2°)	Center for Epidemiologic Studies Depression Scale (CES-D) (continuous) at 4-, 8-, and 12-month follow-up visits and using cutoff ≥ 16 (binary) at 4-, 8-, and 12-month follow-up
	Anxiety (2°)	Beck Anxiety Inventory (BAI) (continuous) at 4-, 8-, and 12-month follow-up visits and using cutoff ≥ 16 (binary) at 4-, 8-, and 12-month follow-up

	Heavy alcohol use (2°)	Alcohol Use Disorders Identification Test (AUDIT-C) (continuous) at 4-, 8-, and 12-month follow-up and using cutoff ≥ 4 (binary) at 4-, 8-, and 12-month follow-up; Percentage of TLFB-Heavy Drinking Days in the previous 30 days
	Suicidality (2°)	Suicidal Ideation Attributes Scale (SIDAS) (continuous) at 4-, 8-, and 12-month follow-up and using cutoffs ≥ 21 (binary) at 4-, 8-, and 12-month follow-up

Table 2. Exploratory Outcome Measures

Domain	Measure	Source, Frequency, and Sample
HIV-risk behavior	HIV/STI testing	HIV/STI testing (any/none) (besides study-administered testing) over 12 months
	HIV and STI diagnosis	HIV and STI self-reported testing (gonorrhea; chlamydia; syphilis) (besides study-administered testing) over 12 months

Sample size

The primary and secondary outcome measures are summarized in Table 1.

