The Comunică study originally proposed to recruit 326 subjects. This was based on calculations that the study would have 80% power to detect effect sizes ranging from 0.25 to 0.27 if the study attained 80% retention of the study subjects. However, recruitment was slower than planned (due to the COVID-19 pandemic and likely other factors), although retention was better than the 80% estimated.

Therefore, as we approached the end of recruitment for the Comunică study, three factors that were not available when we wrote the proposal transpired: i) While 303 participants were finally enrolled, we had re-estimated that we would likely only be able to recruit 288 subjects by 31 December 2022 (our date of termination of recruitment) and based power re-estimation on this number. ii) The overall participation rate for attending all three post-intervention visits was 86% (with a high proportion of the remaining sample completing 2 post-interventions assessments). iii) From preliminary analysis of our data, we had normative distributions of the study outcomes that could be used in establishing a study design and metrics for powering the primary outcome. To that end, we re-estimated the study power as described below and this new estimate was approved by the Data Safety and Monitoring Board (DSMB).

In the original proposal, a repeated measures mixed linear model (or generalized estimation equation) using all 4 study visits (Baseline, and 4-, 8-, and 12-month follow-ups) was planned. However, the distribution of our primary outcomes (HIV-transmission-risk behavior) based on the data we now had near the end of the study was problematic for fitting this type of model, which is based on a central limit theorem assumption that may not manifest. Namely, there were two issues to consider: 1) at each follow up visit, over 50% of participants manifest no HIV-transmission-risk behavior creating a large point mass at the lower limit of 0. 2) On the other end, the distribution of HIV-transmission-risk behavior acts was very skewed with numbers of acts greater than 50 leading to skewness much > 3 , which again contradicts normality-based methods.

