Due to multiple comparison issues, these will each be tested individually using a two-sided Type-1 error of 0.01 and quantified using 99% confidence intervals.

Levels of these measures at 4-, 8-, and 12-month follow-up will be compared (adjusting for the level at the baseline visit) between the Comunică intervention and EAC group in repeated measures analyses as described below.

4-A For Continuous Outcomes that are Heavily Skewed to the Right and Without an Excessive Point Mass at 0 for 4-, 8-, and 12-months follow-up

We anticipate that BAI and number of heavy drinking days will fall into this category. A similar approach to that described for the Primary Outcome will be used.

4-B For Continuous Outcomes that are not Heavily Skewed to the Right at 4-, 8-, and 12-months follow-up

We anticipate that CES-D and AUDIT-C will fall into this category. We will fit repeated measure linear regression mixed models for outcomes at baseline and 4-, 8-, and 12-months follow-up with subject intercept as a fixed effect, main effects for 4-, 8-, and 12-months and a single interaction term between treatment arm assignment and the timepoint being post intervention delivery. In sensitivity analyses, this will be repeated including all baseline covariates that are statistically associated ($p < 0.05$) with the outcome in univariate models using stepwise selection ($p < 0.05$ to enter $p \geq 0.10$ to leave) into the above-described models. The mean post intervention difference in the outcome between the treatment arms with 95% confidence intervals about this term will quantify intervention effect.

4-C For Binary Outcomes

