We will also look at the following binary outcomes: HIV-transmission-risk behavior > 0 , CES-D ≥ 16 , SIDAS ≥ 21 , SIDAS ≥ 0 , AUDIT-C ≥ 4 in repeated measures model using the post-baseline visit and post intervention visits at 4-, 8-, and 12-month follow-ups. Repeated measures generalized estimation equations will be fit about individual as the cluster using a logit link. The visit number (i.e., 4-, 8-, and 12-months vs. vs. baseline) and treatment arm assignment will be included as main effects, as will the baseline preintervention level of the outcome being modeled. In sensitivity analyses, this will be repeated including all baseline covariates that are statistically associated ($p < 0.05$) with the outcome using Stepwise selection ($p < 0.05$ to enter $p \geq 0.10$ to leave) into the above-described models. The intervention effect will be quantified by Odds Ratios with 95% confidence intervals.

We will also use exact tests to compare treatment arms for having been ever diagnosed during the single timepoint 12-month study follow up with HIV, syphilis, chlamydia, and gonorrhea.

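### SAP Section 4 sets 0.01 tests and 99% intervals for secondary outcomes, but 4-B and 4-C report the same effects with 95% intervals

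*SAP*

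**What the plan says.** SAP Section 4 lists the secondary measures (CES-D, BAI, SIDAS, AUDIT-C and percentage of heavy drinking days). It then gives one rule for all of them, with multiplicity as the reason: "these will each be tested individually using a two-sided Type-1 error of 0.01 and quantified using 99% confidence intervals". Three subsections describe the models.

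- **4-A** (BAI and heavy drinking days expected) states no level of its own: "A similar approach to that described for the Primary Outcome will be used". The primary-outcome text in Section 3 uses a two-sided 0.05 threshold and a 95% interval.
- **4-B** is for scores that are not heavily skewed: "We anticipate that CES-D and AUDIT-C will fall into this category". It ends: "The mean post intervention difference in the outcome between the treatment arms with 95% confidence intervals about this term will quantify intervention effect".
- **4-C** covers the "following binary outcomes: HIV-transmission-risk behavior > 0 , CES-D ≥ 16 , SIDAS ≥ 21 , SIDAS ≥ 0 , AUDIT-C ≥ 4". It ends: "The intervention effect will be quantified by Odds Ratios with 95% confidence intervals".

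Neither 4-B nor 4-C states an exception to the Section 4 rule or calls its 95% intervals additional or descriptive. The p-value cutoffs in these subsections (0.05 to enter, 0.10 to leave) concern covariate selection, not the treatment effect.

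**The concern.** The general rule and the subsections assign different confidence levels to the same treatment effects. An analyst writing the table shells must choose one without guidance.

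The choice affects how results are read. A 99% interval agrees with a 0.01 test: it excludes no effect when the test rejects. A 95% interval agrees with a 0.05 test. If 4-B and 4-C are followed as printed, a depression, suicidality or alcohol result with 0.01 < p < 0.05 would be declared not significant in the text, while its interval in the table lies wholly on one side of no effect. Many readers judge from the interval and would take that as a positive finding. The Section 4 rule was written to prevent this.

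**Working it through.** **1. Is the Section 4 rule consistent with itself?** The alpha implied by a confidence level is 1 − level. For 99% this is 1 − 0.99 = 0.01, which matches the stated test level. It also equals 0.05/5 for the five listed measures, although the SAP does not say that this is how 0.01 was reached. For 95% the implied alpha is 1 − 0.95 = 0.05, which does not match.

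**2. Which effects are in conflict?**

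| Place | Effects | Section 4 rule | Subsection |
|---|---|---|---|
| 4-A | BAI score, heavy drinking days | 99% | none stated; refers to the primary-outcome approach |
| 4-B | CES-D score, AUDIT-C score | 99% | 95% |
| 4-C | CES-D ≥ 16, SIDAS ≥ 21, SIDAS ≥ 0, AUDIT-C ≥ 4 | 99% | 95% |
| 4-C | HIV-transmission-risk behavior > 0 | not covered | 95% |

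Direct conflicts: 2 + 4 = 6. The last row is not one of them, because SAP Table 1 makes the binary form a supportive analysis of the primary outcome. The count reads SIDAS ≥ 0 as the any-score-above-zero cutoff in the Section 4 list; as printed in 4-C, it would include every participant.

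**3. Interval width.** The critical values are z(0.995) = 2.576 and z(0.975) = 1.960, so the ratio is 2.576/1.960 = 1.314. This applies on the model scale (log odds for 4-C).

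**4. How often would test and interval disagree?** Take Z ~ N(d, 1), with the test and the interval built from the same estimate and standard error. Disagreement means 0.01 < p < 0.05, that is 1.960 < |Z| < 2.576.

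- No true effect, d = 0: 0.05 − 0.01 = 0.040.
- An effect that a 0.05 test detects with 80% power, d = 1.960 + 0.842 = 2.802: power is 0.800 at 0.05 and 0.589 at 0.01, so 0.800 − 0.589 = 0.211.
- Worst case, d midway between the critical values, (1.960 + 2.576)/2 = 2.268: 0.242.

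These probabilities hold for any pairing of a 0.01 test with a 95% interval and use no trial data.

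**5. Rough scale for the 4-B scores.** Assume an unadjusted difference between two equal groups in SD units, with SE = √(2/n) for n per arm.

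- n = 123 (SAP, Sample size): SE = √(2/123) = 0.1275. Half-widths are 1.960 × 0.1275 = 0.250 and 2.576 × 0.1275 = 0.328.
- The SAP also says "While 303 participants were finally enrolled". With its 86% attendance at all three follow-ups, 303 × 0.86 = 260.6, or 130.3 per arm. SE = √(2/130.3) = 0.1239, with half-widths 0.243 and 0.319.

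Observed differences of about 0.25 to 0.33 SD (or 0.24 to 0.32 SD) would therefore fall in the gap. The Sample size section plans around effects of similar size for the primary outcome (0.25 to 0.27, later 0.33). Baseline adjustment and repeated measures would shift the band, so it shows scale only.

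**The case against.** - **The 95% sentences may cover only the sensitivity analyses.** In both 4-B and 4-C they directly follow the sentence on covariate-adjusted sensitivity models, which could leave 99% for the main analyses. The position is as described, but the wording is general and speaks of the intervention effect without restriction. On this reading 4-B and 4-C would name no effect measure for their main analyses, and adjusted and unadjusted results would carry different levels without explanation. It is the weaker reading.
- **Both levels could be printed.** An analyst could test at 0.01 and show a 99% and a 95% interval side by side, which would satisfy every sentence. That is possible, but the SAP does not say it.
- **The decision rule is untouched.** This stands. The 0.01 level is not contradicted anywhere, and no model, estimate, sample size or power figure changes. The point concerns reporting and does not show an inflated error rate.
- **The count of six is provisional.** This stands in part. Assignment to 4-B is only anticipated, and a score that proves skewed would move to 4-A, which states no level. The count also relies on the SIDAS reading given above. The conflict remains for whatever stays in 4-B and for the other binary cutoffs.

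**Conclusion.** The SAP is wrong as written: Section 4 and its subsections 4-B and 4-C give different confidence levels for the same six secondary effects, and the 95% intervals do not match the 0.01 test. The planned type 1 error is unchanged. For each effect, the chance that the planned test fails while the printed interval excludes no effect is 4% with no true effect, 21% at an effect with 80% power at 0.05, and never more than 24%. These figures assume a normal test statistic shared by the test and the interval. Section 4-A needs clarification only. HIV-transmission-risk behavior > 0 is not affected. The correction should be made, because it governs how the secondary results are read; it does not bear on the primary conclusion.

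**What to change.** - **4-B:** change 95% to 99%.
- **4-C:** change 95% to 99% for the secondary outcomes. Keep 95% for HIV-transmission-risk behavior > 0, and say that this is because it is a supportive form of the primary outcome.
- **4-A:** add that the Section 4 rule (two-sided 0.01, 99% interval) applies.

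A sentence under the Section 4 rule saying that it covers every secondary outcome would also reach the SIDAS score and BAI ≥ 16, which Section 4 lists but no subsection names. If the team also wants 95% intervals, they should appear beside the 99% intervals and be labelled descriptive.

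The cost is SAP wording. The change applies a level the SAP already states and needs no new data, model or test level. Secondary intervals become about 1.31 times as wide on the model scale, and any output already produced at 95% must be re-printed.

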Importantly for power estimation, the correlation of baseline and the average 12-month HIV-transmission-risk behavior acts was 0.37, which means that after adjustment for the pre-intervention behavior, the standard deviation of the post-intervention behavior would be the square root of $(1-0.37^2) = 0.93$ that of the unadjusted outcome. Based on this and with 288 subjects, 86% of whom participated in all 3 visits as we have been observing will happen (or conservatively 123 in each treatment arm), there is 80% power to detect an effect size of 0.33, slightly greater than our originally estimated effect size of 0.25-0.27 and at the upper end of the range of effect sizes found for behavioral interventions addressing multiple health outcomes among sexual minority men (Pantalone et al., 2020). We believe that 0.33 represents a plausible effect size to detect in this trial given the strong distinction between the two intervention conditions, with one involving an active therapist-guided intervention and the other consisting of self-guided psychoeducation only. The standard deviation of the (Winsorized)

averaged outcome over 12 months per-assessment HIV-transmission-risk behavior acts was 3.46 acts. Multiplying this standard deviation by the effect size of 0.33 gives 1.14 HIV-transmission-risk behavior acts. This means that the study will have 80% power to detect an overall mean reduction of 1.14 HIV-transmission-risk behavior acts in the prior 30 days per assessment period in the intervention compared to the control condition.

It should be noted that our final analysis will most likely incorporate the partial information from men with only 1 and 2 post-intervention follow-up visits through imputations or more exactly adjustment of the partial information for number of trimesters reported. If so, this would increase power, by a very modest amount.

DRAFT ANALYTIC PLAN FOR COMUNICĂ STUDY

1. Overview

The analysis of the primary and secondary outcomes will use intent-to-treat with participants analyzed according to their original treatment assignment. SAS 9.4, SPSS 26.0, Stata and/or R software will be used for all analyses.

2. Comparability of Treatment Groups

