Differences in baseline demographic characteristics between the two treatment arms will be assessed using appropriate graphical and statistical methods including summary statistics and p -values from exact, rank, chi-square, t -tests and ANOVA. Of note, later on in the analysis, we will control for variables related to the study outcome in the analyses. We will also investigate if the randomization scheme was compromised.

3. Analysis of Primary Outcome: Number of condomless anal sex acts in the past 30 days with HIV-positive or unknown-status partners outside of the context of one's own adherent PrEP use or primary partner's adherent PrEP use or undetectable viral load in the past 30 days (HIV-transmission-risk behavior)

The statistical significance threshold for an intervention (vs. control) arm effect will be a two-sided $p \leq 0.05$. The primary outcome will be evaluated between the treatment arms at 4-, 8-, and 12-month follow-ups combined in a repeated measures analysis that adjusts for baseline behavior. This will be analyzed using negative binomial regression with baseline, and 4-, 8-, and 12-month follow-ups clustered within the same person. Main effect terms for 4-, 8-, and 12-month follow-ups post-baseline (each timepoint vs. baseline) will be included in the model. A single interaction term between the 4-, 8-, and 12-month measures with the intervention arm will be included in the model to test for pooled post-baseline treatment arm differences. The relative number of HIV-transmission-risk behavior acts with a 95% confidence interval about this term will quantify intervention effect. Generalized estimating equations with person as the cluster will be used to account for within person repeated measure collinearity. As a sensitivity analysis, this will be repeated including all baseline covariates that are statistically associated ($p < 0.05$ to enter and $p \geq 0.10$ to leave in a stepwise selection) with HIV-transmission-risk behavior in negative binomial GEE models with person as the cluster and adjusting for time of visit (i.e. 4-, 8-, and 12 months each vs. baseline).

If there are excess zeros at each post-baseline visit, we will consider using a zero-inflated negative binomial model instead. However, this approach will split the intervention effect

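### SAP 4-B names a mixed model for continuous CES-D and AUDIT-C but fixes the subject intercept and states no within-person covariance; followed as written, it loses precision, empties its covariate sensitivity analysis and can miss its 0.01 error rate

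*SAP*

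**What the plan says.** SAP section 4-B covers continuous outcomes that are not heavily skewed and expects CES-D and AUDIT-C to be among them. It opens: "We will fit repeated measure linear regression mixed models for outcomes at baseline" and the three follow-ups. The same sentence lists the terms: "with subject intercept as a fixed effect, main effects for 4-, 8-, and 12-months and a single interaction term", that interaction being arm by post-intervention. No arm main effect, random effect, residual covariance or robust variance is listed.

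Three other statements bear on it:
- The lead-in to the secondary analyses says the arms are compared with adjustment for the baseline level, and that "these will each be tested individually using a two-sided Type-1 error of 0.01".
- The next step in 4-B is a sensitivity analysis: "this will be repeated including all baseline covariates that are statistically associated" with the outcome.
- For the primary outcome, section 3 does say how repeated measures are handled: "Generalized estimating equations with person as the cluster will be used to account for within person repeated measure collinearity". Section 4-C likewise clusters on the individual.

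**The concern.** A mixed model needs a random component or a modelled covariance, and 4-B supplies neither. If the subject intercepts are fixed, each participant serves only as his own control. Three things then follow.

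1. The baseline slope is set to 1 instead of being estimated, which costs precision for two outcomes tested at a strict threshold.
2. Anything constant within a participant, including every baseline covariate, is already explained by his intercept.
3. Residuals around that intercept are treated as independent. This is wrong if the three follow-ups resemble each other more than they resemble baseline.

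At stake are the width of two secondary intervals, the usefulness of one pre-specified sensitivity analysis, and whether the 0.01 test has its stated error rate.

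**Working it through.** **The plan's own figure.** The SAP gives no power, SD or correlation for CES-D or AUDIT-C. The nearest figure is for the primary outcome in the Sample size section: 80% power for 0.33 SD, "conservatively 123 in each treatment arm", correlation 0.37 between baseline and mean follow-up, two-sided 0.05. Residual SD = √(1 − 0.37²) = 0.929. Detectable effect = (1.960 + 0.842) × 0.929 × √(2/123) = 0.332, and power at 0.33 is 79.5%. The figure reproduces. It relies on an estimated baseline slope; without that adjustment power would be 73.5%.

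**Inputs for 4-B.** 123 per arm and alpha 0.01 come from the SAP. The within-person correlation r is assumed, so a range is shown. Outcome variance is set to 1 at each visit, with one baseline, three follow-ups and complete data.

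**Precision, equal correlation r.**
- Fixed intercept: the arm term is the difference in (mean of follow-ups − baseline). V_fixed = 4(1 − r)/3.
- Random intercept, same terms, no arm main effect: V_random = (1 − r)(1 + 3r)/3.
- Relative efficiency = V_random/V_fixed = (1 + 3r)/4.
- Detectable difference at 80% power = (2.576 + 0.842) × √(2V/123).
- Power of the fixed model at the difference the random model detects with 80% power = Φ(3.418 × √ratio − 2.576).

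| r | Ratio | Information lost | Interval wider by | Detectable, fixed vs random (SD) | Power of fixed | Equivalent N of 246 |
|---|---|---|---|---|---|---|
| 0.5 | 0.625 | 37.5% | 26% | 0.36 vs 0.28 | 55% | 154 |
| 0.7 | 0.775 | 22.5% | 14% | 0.28 vs 0.24 | 67% | 191 |
| 0.8 | 0.850 | 15% | 8% | 0.23 vs 0.21 | 72% | 209 |

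The interval column is 1/√ratio − 1 and applies at any confidence level.

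**Sensitivity analysis.** With 246 participants, the subject intercepts, 3 visit terms and 1 post × arm term make 246 + 3 + 1 = 250 columns, of rank 250. Adding one baseline covariate gives 251 columns but still rank 250. In simulated data the arm estimate with and without the covariate agreed to within 1e-14. The same held with 14% of participants missing one follow-up. This result needs no assumption about r.

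**Error rate, unequal correlations.** Let c be the baseline-to-follow-up correlation and p the correlation between follow-ups.
- True variance of the fixed-intercept contrast: (1 + 2p)/3 + 1 − 2c.
- Variance the literal model reports: with independent residuals it pools all within-person variation, so residual variance = 1 − (c + p)/2 and reported variance = 4/3 of that.
- Null rejection at nominal 0.01: 2Φ(−2.576 × √(reported/true)).

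For c = 0.5, p = 0.7: true 0.800; reported 4/3 × 0.40 = 0.533; ratio 0.667; rejection 3.5%.
For c = 0.7, p = 0.8: true 0.467; reported 4/3 × 0.25 = 0.333; ratio 0.714; rejection 3.0%.

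A random intercept alone uses the pooled correlation r̄ = (c + p)/2 as its slope. Its true variance is (1 + 2p)/3 + r̄² − 2r̄c and its reported variance is (1 − r̄)(1 + 3r̄)/3. At (0.5, 0.7) these are 0.560 and 0.373, and at (0.7, 0.8) they are 0.379 and 0.271. The ratios are again 0.667 and 0.714, so the inflation is the same. Simulation agreed: about 3.3% and 3.0% for the literal model, 3.4% and 3.0% for the random intercept, and about 1.2% with an unstructured covariance.

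**Precision, unequal correlations.** Against a freely estimated slope, with variance (1 + 2p)/3 − c², the fixed intercept loses 1 − 0.550/0.800 = 31% at (0.5, 0.7) and 1 − 0.377/0.467 = 19% at (0.7, 0.8).

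**The case against.** The strongest reply is that fixed is a slip for random and nobody will fit the literal model. There is good evidence for that. The sentence itself says mixed, section 4 promises baseline adjustment, the next step adds covariates that would otherwise do nothing, and the Sample size section says the original proposal planned "a repeated measures mixed linear model (or generalized estimation equation) using all 4 study visits". If so, the precision loss disappears and what remains is an unclear model statement. That part stands, and it is why the loss is stated conditionally. It does not close the point. The SAP allows several software packages, so no default settles the reading, and changing fixed to random still leaves the covariance unstated and the 0.01 test exposed.

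It is also fair that the size rests on an undocumented correlation, that the loss is modest at high r, and that the gain from a random intercept depends on leaving out an arm main effect. With that term added, the two models agreed in complete data. 4-B does leave it out.

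A reader might infer more than the documents support:
- *That the arm estimate is biased.* It is not; simulated means matched the true effect.
- *That collinearity makes the arm effect inestimable.* It does not; only the covariate coefficients are unidentified.
- *That using baseline as an outcome row is the error.* Section 3 uses the same layout and describes it as "combined in a repeated measures analysis that adjusts for baseline behavior".
- *That the error rate always fails.* Under equal correlations the literal model is close to nominal.

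**Conclusion.** The specification is internally inconsistent and, if followed, gives a worse analysis than the plan intends. The empty covariate sensitivity analysis follows from the literal text with no numerical assumption. The information loss of 15% to 37.5% assumes the literal reading, complete data and equal correlations between 0.8 and 0.5. The rejection rate of about 3% at nominal 0.01 assumes model-based standard errors and follow-ups that correlate more with each other than with baseline. It applies to the literal model and equally to a plain random intercept.

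The reach is two secondary outcomes, continuous CES-D and AUDIT-C. The primary analysis, the 4-A outcomes and the binary models use GEE with the person as cluster and are unaffected. It should be fixed, but it does not threaten the trial's main conclusion.

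**What to change.** In 4-B, replace the words that make the subject intercept fixed with a statement that the model uses an unstructured within-person covariance across the four visits. A random subject intercept with cluster-robust standard errors is an acceptable alternative; a random intercept with model-based standard errors is not enough. Keep the visit effects and the single post × arm term, and say explicitly that there is no arm main effect.

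Baseline then carries an estimated weight, the covariate-adjusted analysis can differ from the main one, and the test does not depend on equal correlations. The cost is one phrase in the SAP and no new data. If a mixed model was always intended, the change mainly records that intention and names the covariance.

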**Building Mobile HIV Prevention and Mental Health Support in Low-resource
Settings**

NCT #: NCT03912753

July 8, 2024

Statistical Analysis Plan

Introduction

The current study aims to test the efficacy of Comunică, a motivational interviewing intervention also informed by minority stress theory, to reduce HIV-transmission-risk behavior in a randomized controlled trial among Romanian gay and bisexual men (GBM). In this study, the primary outcome involves HIV-transmission-risk behavior. Secondary outcomes include depression, anxiety, heavy alcohol use, and suicidality. Exploratory outcomes include HIV and STI (chlamydia, gonorrhea, syphilis) diagnosis and HIV/STI testing patterns. The control condition, referred to as “educational attention control (EAC)” consists of eight educational modules that present information regarding GBM’s identity development, HIV/STI prevention, heavy alcohol use and its associations with HIV-transmission-risk behavior, sexual health communication, and the importance of social support. This EAC was created in consultation with Romanian GBM community members and advocates.

Study Design

In this RCT, Comunică is compared to EAC to examine relative change in: (a) the primary outcome, HIV-transmission-risk behavior defined as: frequency of condomless anal sex acts with HIV-positive or unknown-status partners outside of the context of one’s own adherent PrEP use or only with a primary partner that has adherent PrEP use or has undetectable viral load and (b) secondary outcomes: depression, anxiety, heavy alcohol use, and suicidality. Sessions for both conditions are to be completed over the course of four months. Outcomes are measured by self-report at pre-intervention (baseline), and at 4-, 8-, and 12-month follow-ups. At baseline and 12-month follow-up, all participants also self-administer at-home rapid testing for HIV and syphilis, and self-collect sampling (urethral, pharyngeal, rectal) for chlamydia and gonorrhea, which are sent to a laboratory for analyses.

Table 1. Primary and Secondary Outcome Measures

Domain	Measure (1°, 2°)	Source, Frequency, and Sample

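### SAP 4-B and 4-C give 95% intervals for secondary outcomes that Section 4 tests at 0.01 with 99% intervals; 4-C also has three wording errors

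*SAP*

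**What the plan says.** **Interval level.** Before sub-section 4-A, SAP Section 4 cites multiple comparisons and sets a two-sided type I error of 0.01 with 99% confidence intervals for each secondary outcome. Section 4-B then asks for 95% intervals around the mean difference, and 4-C for 95% intervals around the odds ratio. Section 4-A gives no level but refers to the primary-outcome approach, and Section 3 reports that with a 95% interval.

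**Binary outcomes.** The list in 4-C includes "SIDAS ≥ 21 , SIDAS ≥ 0 , AUDIT-C ≥ 4". The outcome list in Section 4 instead defines the second SIDAS outcome as a score above 0, and Table 1 gives only the cutoff of 21. BAI at or above 16 is in Table 1 and in the Section 4 list, but not in 4-C.

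**Model in 4-C.** The rows are described as "using the post-baseline visit and post intervention visits at 4-, 8-, and 12-month follow-ups". On visit and arm, 4-C says "The visit number (i.e., 4-, 8-, and 12-months vs. vs. baseline) and treatment arm assignment will be included as main effects". It then adds the pre-treatment value of the same outcome as a predictor. The lead-in to all of Section 4 reads "Levels of these measures at 4-, 8-, and 12-month follow-up will be compared (adjusting for the level at the baseline visit".

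**The concern.** The interval and the test for a secondary outcome should lead to the same conclusion. With a 95% interval beside a 0.01 test, any result with p between 0.01 and 0.05 has an interval that excludes the null although the outcome is not significant under the plan's own rule. Readers look at the interval first, so the multiplicity protection is weakened where it is most visible.

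The faults in 4-C are smaller but leave choices open after the data are seen. Taken literally, one listed outcome may have no variation, one prespecified outcome has no stated model, and the visit wording calls for baseline as an outcome row while the other terms suit a model of follow-up visits only.

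**Working it through.** **1. Interval level against test level.** A 99% interval corresponds to 1 − 0.99 = 0.01, which matches the rule in Section 4. A 95% interval corresponds to 1 − 0.95 = 0.05, which does not. The normal multipliers are 2.576 and 1.960, and 2.576 / 1.960 = 1.31.

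**2. Chance of a mismatch for one analysis.** This is P(1.960 < |Z| ≤ 2.576), with Z normal with variance 1:

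| Situation | Mean of Z | Probability |
|---|---|---|
| No effect | 0 | 0.040 |
| Worst case | 2.268 | 0.242 |
| 80% power at 0.05 | 2.802 | 0.211 |
| 80% power at 0.01 | 3.417 | 0.128 |

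**3. Chance of at least one mismatch, no effect anywhere.** Once the list is corrected, 4-B and 4-C hold 7 secondary analyses: CES-D and AUDIT-C as continuous; CES-D ≥ 16, BAI ≥ 16, SIDAS ≥ 21, SIDAS > 0 and AUDIT-C ≥ 4 as binary. If independent, 1 − 0.96^7 = 0.249. With pairwise correlation 0.3, 0.5 and 0.7, simulation gives 0.23, 0.21 and 0.17.

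Adding continuous BAI and heavy drinking days (4-A), and continuous SIDAS (named in neither 4-A nor 4-B), makes 10. If independent and all reported with 95% intervals, 1 − 0.96^10 = 0.335, about 34%.

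**4. SIDAS and BAI.** No arithmetic is needed. The phrase about scores above 0 implies that 0 is the lowest SIDAS score, though the SAP does not say so. If it is, every participant meets ≥ 0 and no odds ratio can be estimated. For BAI, 4-C includes the cutoffs of the other three scales and leaves out only this one.

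**5. Which rows 4-C models.** A visit contrast against baseline needs baseline as an outcome row. A baseline covariate with arm as a main effect suits follow-up rows only. The SAP's Study Design section says "Outcomes are measured by self-report at pre-intervention (baseline), and at 4-, 8-, and 12-month follow-ups", so no separate post-baseline visit exists. Where the plan does want baseline as a row, it says so: Section 3 has "negative binomial regression with baseline, and 4-, 8-, and 12-month follow-ups clustered within the same person" and 4-B has "We will fit repeated measure linear regression mixed models for outcomes at baseline and 4-, 8-, and 12-months follow-up". Both pair this with an arm-by-post-baseline term, which 4-C lacks. Together with the lead-in, this favours follow-up only.

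**6. Size, if baseline were kept as a row.** The documents give no prevalences for the binary secondary outcomes, so these are assumed. The model is logistic with a normal random intercept (SD 1, 1.5 or 2) and a conditional log odds ratio of −0.8. Expected response-pattern frequencies were used, and the GEE was solved with independence working correlation. Baseline / control follow-up prevalences were 15/12, 30/25, 50/42, 70/60 and 90/85%.

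- The log odds ratio with the baseline row is 0.741 to 0.946 of the follow-up-only value.
- Follow-up-only against baseline-row odds ratios are 0.48 and 0.58 (15%, SD 1), 0.54 and 0.58 (50%, SD 1.5), and 0.57 and 0.60 (70%, SD 2).

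For HIV-transmission-risk behavior > 0 the documents do bear on prevalence. Protocol Eligibility requires at least one condomless act with an HIV-positive or unknown-status partner in the prior month and no current PrEP use, so baseline should be high. The SAP's Sample size section puts more than half of participants at zero at each follow-up visit. With an assumed 95 to 98% at baseline and 45% at follow-up, the ratio is 0.965 to 0.995. At 98% and SD 1.5 the odds ratios are 0.563 and 0.566.

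**The case against.** The strongest reply is that the intended plan can be recovered. The 0.01 and 99% rule is explicit and heads the section. The lead-in and the baseline covariate settle the 4-C model, leaving only stray wording. The Section 4 list shows that SIDAS > 0 was meant. BAI ≥ 16 is prespecified twice, and 4-C is headed as the section for binary outcomes. Most of this stands for the three 4-C points, which is why they are lesser ones. It does not remove the interval conflict: 4-B and 4-C are the operative instructions for reporting, and an analyst cannot follow both them and the opening rule.

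A reader might infer more than the documents support:

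- **That the secondary type I error is 0.05 per test.** The testing rule is 0.01. The figures above are chances that interval and test disagree, not chances of a false claim. The error would rise to 0.05 only if conclusions were drawn from the 95% intervals.
- **That all odds ratios in 4-C would be pulled noticeably toward 1.** This needs baseline as an outcome row, the less supported reading. Even then it hardly touches HIV-transmission-risk behavior > 0.
- **That the SIDAS outcome has three competing definitions, or that binary BAI was dropped.** Table 1 omits one cutoff and 4-C appears to mistype it; the BAI omission is from a list only.
- **That every 95% interval in 4-C is wrong.** Table 1 calls HIV-transmission-risk behavior > 0 supportive of the primary outcome, so 95% can be right there.

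**Conclusion.** The point holds, with the interval level as its core. Sections 4-B and 4-C contradict the opening of Section 4, and 4-A inherits the doubt. The 1.31 width ratio, the 4% per analysis with no effect and the 24% ceiling need no prevalence assumption, only approximate normality of the test statistic. The 25% (7 analyses) and 34% (10 analyses) also assume independence and no true effects; positive correlation lowers them. Type I error stays at 0.01 per analysis only if the opening rule governs the conclusions.

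The three faults in 4-C are lesser and their intent can be read elsewhere in the SAP. The 0.74 to 0.95 ratio rests on assumed prevalences, random-intercept SDs and independence working correlation, and applies only if baseline is kept as a row with arm as a main effect. The Section 3 primary analysis and its stated power are not affected. The plan should be corrected, but no design decision turns on it.

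**What to change.** - **4-A, 4-B and 4-C:** state 99% confidence intervals for every secondary outcome, including continuous SIDAS wherever it is placed. Keep 95% only for HIV-transmission-risk behavior > 0.
- **SIDAS:** write SIDAS > 0 in 4-C and list it in Table 1.
- **BAI:** add BAI ≥ 16 to the list in 4-C.
- **4-C model:** use only the 4-, 8- and 12-month visits as outcome rows, with visit (8 and 12 against 4 months), arm, and the baseline value as covariate. Delete the contrast against baseline and the mention of a post-baseline visit.

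The cost is SAP wording and reported secondary intervals 1.31 times as wide. No new data are needed.
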